5.1.3 Concomitant medication date imputation

The imputation of a concomitant medication start date will follow the same conventions as for an AE start date (see [Section 5.1.2](#)). No imputation will be performed for concomitant medication end dates.

5.1.3.1 Prior therapies date imputation

Start date

The same rule which is applied to the imputation of AE/concomitant medication start date will be used with the exception that scenario (B) will be replaced to be 'start date of study treatment - 1' (see [Section 5.1.2](#)).

End date

Imputed date = min (start date of study treatment, last day of the month), if day is missing;

Imputed date = min (start date of study treatment, 31DEC), if month and day are missing.

If the end date is not missing and the imputed start date is after the end date, use the end date as the imputed start date.

If both the start date and the end date are imputed and if the imputed start date is after the imputed end date, use the imputed end date as the imputation for the start date.

5.1.3.2 Post therapies date imputation

Start date

Imputed date = max (End of Treatment date + 1, first day of the month), if day is missing;

Imputed date = max (End of Treatment date + 1, 01JAN), if day and month are missing.

Imputed date = End of treatment date +1, if the date is completely missing.

End date

No imputation

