Following approval of protocol amendment 03, the efficacy and safety assessments will be performed as per each institution's standard of care. The assessment schedule in [Table 8-2](#) will no longer be applicable and will be replaced by [Table 8-2b](#).

The Assessment Schedule ([Table 8-2](#)) lists all of the assessments when they are performed. All data obtained from these assessments must be supported in the subject's source documentation.

Subjects should be seen for all visits/assessments as outlined in the assessment schedule ([Table 8-2](#)) or as close to the designated day/time as possible. Missed or rescheduled visits should not lead to automatic discontinuation. Subjects who prematurely discontinue the study for any reason should be scheduled for a visit as soon as possible, at which time all of the assessments listed for the final visit will be performed. At this final visit, all dispensed investigational product should be reconciled, and the adverse event and concomitant medications recorded on the eCRF.

During the course of the study visits, test procedures should occur on schedule whenever possible as per allowable visit windows specified in [Table 8-1](#) below.

As per [Section 4.6](#), during a public health emergency as declared by local or regional authorities i.e. pandemic, epidemic or natural disaster that limits or prevents on-site study visits, alternative methods of providing continuing care may be implemented by the investigator as the situation dictates. If allowed by local Health Authority and depending on operational capabilities, phone calls or virtual contacts (e.g. tele consult) can replace on-site study visits, for the duration of the disruption until it is safe for the participant to visit the site again.

Table 8-1 Allowable visit windows

Visit name	Window
Screening	Day -28 to Day -1
Cycle 1 Day 1	Within 3 days after randomization in IRT
Day 1 of the subsequent cycles	± 4 Days
PK/IG/PD sampling	Refer to tables in Section 8.5.1
Tumor assessments	± 7 Days
EOT	≤ 7 Days after decision of discontinuation of study treatment
Safety follow up assessment	± 7 Days
Survival follow- up	± 14 Days

Table 8-2 Assessment Schedule – obsolete upon approval of protocol amendment 03

Period	Screening	Treatment								Follow-up		
Visit Name	Screening	Cycle 1	Cycle 2	Cycle 3	Cycle 4	Cycle 5	Cycle 6	Subsequent cycles (Up to 35 cycles)	EOT	Safety	Disease progression	Survival
Day	-28 to -1	1	1	1	1	1	1	1	-	30	-	Every 12 weeks

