9.2.2.2 Disease progression follow-up

Following approval of protocol amendment 03, disease progression follow-up will not be performed.

All subjects who discontinue study treatment for any reason other than death or disease progression as per RECIST 1.1 should return for tumor assessments at the intervals specified in [Table 8-2](#) until documented disease progression, death, lost to follow-up or withdrawal of consent ([Section 8.3.1](#)).

If patients refuse to return for these visits or are unable to do so, every effort should be made to contact them or a knowledgeable informant by telephone to determine if the patient had disease progression. Once the follow-up for disease progression period has ended, the appropriate disposition eCRF should be completed.

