16.1.4.5.3 Incomplete dates for last known date patient alive or death

All dates must be completed with day, month and year. If the day is missing, the 15th of the month will be used for incomplete death dates or dates of last contact.

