2.5.3 Handling of missing values/censoring/discontinuations

PFS will be censored at the date of the last adequate tumor assessment prior to the earliest cut-off date for the analysis, the start of a subsequent anti-neoplastic therapy (if any), the date of sponsor's decision to discontinue capmatinib (applicable only to subjects on the combination arm), or if the event occurred after two or more missing tumor assessments. Clinical progression without objective radiological evidence will not be considered as documented disease progression. Subjects should be followed after discontinuation of treatment to document clinical progression. The date of the last adequate tumor assessment is the date of the last tumor assessment with overall lesion response of CR, PR or SD before an event or a censoring reason has occurred. If no post-baseline assessments are available (before an event or a censoring reason occurred), the date of treatment randomization will be used.

The number of subjects censored and reasons for censoring will be summarized by treatment arm using descriptive statistics.

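### Incomplete start dates of post-treatment cancer therapy are imputed to the earliest admissible day, which can turn a progression documented after end of treatment into an earlier censored PFS time; separately, the mid-month rule for deaths can give an impossible date

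*SAP*

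**What the plan says.** SAP 5.1.3.2 has three rules for the start of therapy given after study treatment:

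- day missing: "Imputed date = max (End of Treatment date + 1, first day of the month), if day is missing"
- day and month missing: "Imputed date = max (End of Treatment date + 1, 01JAN), if day and month are missing"
- nothing recorded: "Imputed date = End of treatment date +1, if the date is completely missing"

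SAP 2.5.3 (like protocol 12.4.1.3) makes the start of subsequent anti-neoplastic therapy a reason to censor PFS. The censoring date is that of the "last tumor assessment with overall lesion response of CR, PR or SD before an event or a censoring reason has occurred". DOR takes over the same rules (SAP 2.7.3).

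Before amendment 03, scans continued after treatment stopped. Protocol 9.2.2.2 reads: "All subjects who discontinue study treatment for any reason other than death or disease progression as per RECIST 1.1 should return for tumor assessments". Later therapies were asked about in 12-weekly telephone calls (protocol 9.2.2.3).

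For deaths with the day missing, protocol 16.1.4.5.3 states that "the 15th of the month will be used for incomplete death dates or dates of last contact". SAP 2.1.1.6 allows partial dates of death to be imputed and adds no check against other dates.

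**The concern.** Each therapy rule picks the earliest day that the recorded information and the EOT + 1 floor allow. A progression that falls between that day and the true start of therapy then counts as coming after the therapy. Under the censoring rule the event disappears, and follow-up is cut back to the previous adequate scan. The primary endpoint would lose a documented event because of a missing field on the form. The only supportive PFS analysis (SAP 2.5.4) varies the censoring at the sponsor's decision to stop capmatinib, so nothing in the output would reveal the effect.

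The death rule has a different weakness. It does not remove an event, but it can date a death before a scan or contact that shows the subject alive.

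**Working it through.** The plan gives no figure for this point, so there is none to reproduce. The check applies the rules to illustrative subjects. All calendar dates below are assumptions.

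**Inputs.** The imputed start is the later of EOT + 1 and the first day compatible with the recorded part (SAP 5.1.3.2). Progression (PD) is an event if dated before the imputed start; otherwise PFS is censored at the last adequate scan (SAP 2.5.3). Time is end date minus start date plus 1 (protocol 16.1.4.5.1). EOT is read as the EOT visit or page date. Protocol Table 8-1 places that visit "≤ 7 Days after decision of discontinuation of study treatment", so it normally follows a progression that caused the stop.

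**Common dates.** Randomized 1 Jul 2020; last adequate scan 2 Sep 2020 (63 + 1 = day 64); PD 4 Nov 2020 (126 + 1 = day 127).

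| Subject | Day missing | Day and month missing | Wholly missing |
|---|---|---|---|
| A: stopped for PD, EOT 10 Nov, true start 25 Nov | 11 Nov: event, day 127 | 11 Nov: event, day 127 | 11 Nov: event, day 127 |
| B: stopped for an AE, EOT 15 Sep, true start 25 Nov | 1 Nov: censored, day 64 | 16 Sep: censored, day 64 | 16 Sep: censored, day 64 |
| C: as B, but true start 10 Dec | 1 Dec: event, day 127 | 16 Sep: censored, day 64 | 16 Sep: censored, day 64 |

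Subject A shows that the floor protects a progression dated on or before EOT. B and C show that a progression after EOT is exposed. With only the day missing, it is exposed only when PD and therapy start fall in the same month.

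**Same-month chance.** Assume PD precedes therapy by g days, the start is uniform within the month, and a month has 30.4375 days (SAP 2.1.1.3). The chance that both share a month is then 1 − g/30.4375. For g = 3, 7, 14, 21 and 28 days this gives 0.90, 0.77, 0.54, 0.31 and 0.08.

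**Weight of one lost event.** With n at risk, removing one event multiplies the later Kaplan-Meier curve by 1/(1 − 1/n).

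- n = 20: 1/(1 − 1/20) = 1.053; at S = 0.60, 0.60 × 0.053 = 3.2 percentage points
- n = 10: 1/(1 − 1/10) = 1.111; at S = 0.60, 0.60 × 0.111 = 6.7 percentage points

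Both n and S are assumed. The figures are somewhat too large when other events fall between the backdated censoring and the lost PD, because those events then weigh more.

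**Who could be affected.** The amendment 3 study update gives 76 randomized and 50 ongoing on 15-Mar-2021, so 76 − 50 = 26 were off treatment for any reason. The documents do not say how many stopped before progression, or how many had incomplete therapy dates.

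**Death rule.** Suppose a scan on the 24th shows SD and the death is recorded by month only. The imputed death on the 15th precedes the scan by 24 − 15 = 9 days. In a 31-day month the conflict can reach 31 − 15 = 16 days.

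**The case against.** The strongest reply is that the exposed group is narrow. A subject must have stopped for a reason other than progression, progressed after EOT, started another therapy, and had an incomplete start date recorded. Sites are queried about missing values (protocol 11.2), and data for primary variables are fully verified against source (protocol 11.3), so imputation is a last resort. After amendment 03 neither later therapies nor efficacy results are collected (protocol 9.2.2.1 and 8.3). The analysis is descriptive, with no test. All of this stands and limits the size.

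It can also be said that the imputed date may never reach PFS, since the only stated output for these therapies is a listing (SAP 2.4.3.2) and derivations are specified in a separate document. This stands in part: the link is an inference. But no other rule exists for this date. SAP 2.1.1.6 bars completely imputed dates from the last contact date, and nothing similar is said for PFS.

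The order of events is also truly unknown. If therapy is recorded only as December and PD is on 21 December, 20 of the 31 possible days precede the PD. So keeping the event is also an assumption.

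A reader might infer that the error favors the combination arm, because the amendment 3 rationale reports more AEs and SAEs leading to interruption and/or discontinuation there. The documents do not support that step. The statement combines interruption with discontinuation. One drug may continue when the other is stopped for an AE (protocol 6.7.2). Only the combination arm is also censored at the sponsor's decision on capmatinib, so later progressions there are censored whatever date is imputed, while those in the control arm stay exposed.

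**Conclusion.** The point holds in a limited form. If the imputed date enters PFS, a progression documented after EOT can be replaced by an earlier censored time; in the example, event day 127 becomes censored day 64. It does not hold for progressions dated on or before EOT, so it would be wrong to infer that incomplete therapy dates endanger PFS events in general. The number of subjects is unknown and probably small, and no direction by arm can be claimed. One lost event could move a curve by roughly 3 to 7 percentage points under the assumed 10 to 20 at risk and S = 0.60.

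The conclusion rests on two readings: that the imputed date feeds the censoring rule, and that the EOT date is the visit or page date. If it meant the last dose, progressions found shortly after the last dose would also be exposed.

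The death rule is a separate, smaller defect. The 15th is a midpoint and never turns an event into a censored time, so it is not the same bias, but it can produce an impossible date. Both corrections are worth making because they are cheap and touch the primary endpoint, not because a large effect has been shown.

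**What to change.** 1. **SAP 5.1.3.2 and 2.5.3, for PFS and DOR.** Keep a documented PD as an event unless the recorded part of the therapy date shows that therapy began before the PD. Do not impute a start outside the recorded month or year: with PD on 31 December and therapy recorded as December, the PD stays an event and no January start is created. All other censoring rules remain.
2. **Sensitivity analysis.** Repeat the PFS analysis once with the current earliest-date rule, including for wholly missing dates, so that both orderings are shown. This matters most for wholly missing dates, because there item 1 means that new therapy never censors a PD.
3. **Deaths with the day missing.** Use the later of the 15th and the last known alive date + 1, limited to the recorded month. In the example above, the death moves from the 15th to the 25th.

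The cost is a few lines of SAP text and programming and one additional output. The drawback is that item 1 is itself an assumption about order, which is why item 2 is needed.

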5.1.3.3 Other imputations

5.1.3.3.1 Diagnostic and extent of cancer

When a date is recorded as a partial date, the missing day is imputed to the 15th of the month (e.g., DEC2007 imputed to 15DEC2007), and if the day and month are both missing then to 1st of July of that year (e.g., 2007 imputed to 01JUL2007). Such imputed data will be flagged in the listings.

5.2 AEs coding/grading

AEs are coded using the MedDRA terminology. AEs will be assessed according to the CTCAE version 5.0.

The CTCAE represents a comprehensive grading system for reporting the acute and late effects of cancer treatments. CTCAE grading is by definition a 5-point scale generally corresponding to mild, moderate, severe, life threatening, and death. This grading system inherently places a value on the importance of an event, although there is not necessarily proportionality among grades (a grade 2 is not necessarily twice as bad as a grade 1).

5.3 Laboratory parameters derivations

5.3.1 CTC grading for laboratory parameters

Grade categorization of lab values will be assigned programmatically as per NCI CTCAE version 5.0. The calculation of laboratory CTC grades will be based on the observed laboratory values only, clinical assessments will not be taken into account. The criteria to assign CTC grades are given in Novartis internal criteria for CTC grading of laboratory parameters (see [Table 5-3](#)). The latest available version of the document based on the underlying CTCAE version 5.0 at the time of analysis will be used.

For laboratory tests where grades are not defined by CTCAE version 5.0, results will be graded by the low/normal/high classifications based on laboratory normal ranges.

A severity grade of 0 will be assigned for all non-missing lab values not graded as 1 or higher. Grade 5 is not applicable. For laboratory tests that are graded for both low and high values, summaries will be done separately and labeled by direction, e.g., sodium will be summarized as hyponatremia and hypernatremia.

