8. Must have recovered from all toxicities related to prior systemic therapy to grade ≤ 1 (CTCAE v5.0). Exception to this criterion: subjects with any grade of alopecia
9. Must have adequate organ function including the following laboratory values at the screening visit:
 - Absolute neutrophil count (ANC) $\geq 1.5 \times 10^9/L$ (without growth factor support)
 - Platelets $\geq 100 \times 10^9/L$ (without growth factor support or transfusion)
 - Hemoglobin (Hgb) ≥ 9 g/dL (4 weeks without transfusions or erythropoietin)
 - Calculated creatinine clearance (using Cockcroft-Gault formula) ≥ 45 mL/min
 - Total bilirubin (TBIL) $\leq 1.5 \times$ upper limit of normal (ULN)
 - Aspartate aminotransferase (AST) and Alanine aminotransferase (ALT) $\leq 3 \times$ ULN
 - Alkaline phosphatase (ALP) $\leq 5.0 \times$ ULN
 - International Normalized Ratio (INR) or Prothrombin Time (PT) and Activated Partial Thromboplastin Time (aPTT) or Partial Thromboplastin Time (PTT) $\leq 1.5 \times$ ULN unless the subject is receiving anticoagulant therapy
 - Asymptomatic serum amylase \leq grade 2. Subjects with grade 1 or grade 2 serum amylase at the beginning of the study must be confirmed to have no signs and/or symptoms suggesting pancreatitis or pancreatic injury (e.g., elevated P-amylase, abnormal imaging findings of pancreas, etc.)
 - Serum lipase \leq ULN
 - Fasting plasma glucose ≤ 160 mg/dL (≤ 8.9 mmol/L)
 - Subjects must have the following laboratory values within the laboratory normal limits or corrected to within normal limits with supplements during screening:
 - Potassium
 - Magnesium
 - Phosphorus
 - Total calcium (corrected for serum albumin)

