The following will be reported:

- Summary of notable vital sign values

Table with descriptive statistics at baseline, one or several post-baseline time points and change from baseline to this/these post-baseline time points

12-lead ECG

- 12-lead ECGs including PR, QRS, QT, QTcF intervals and heart rate (HR) will be obtained for each subject during the study. ECG data will be read and interpreted locally.
- A listing of these subjects will be produced (by treatment arm).

Clinical laboratory evaluations

All laboratory data will be listed by treatment arm, subject, and visit/time and if normal ranges are available abnormalities will be flagged. Summary statistics will be provided by treatment and visit/time. Shift tables using the low/normal/high/ (low and high) classification will be used to compare baseline to the worst on-treatment value.

Grading of laboratory values will be assigned programmatically as per NCI Common Terminology Criteria for Adverse Events (CTCAE) version 5.0. The calculation of CTCAE grades will be based on the observed laboratory values only, clinical assessments will not be taken into account.

CTCAE Grade 0 will be assigned for all non-missing values not graded as 1 or higher. Grade 5 will not be used.

For laboratory tests where grades are not defined by CTCAE v5.0, results will be categorized as low/normal/high based on laboratory normal ranges.

The following summaries will be generated separately for hematology, and biochemistry tests:

- Listing of all laboratory data with values flagged to show the corresponding CTCAE v5.0 grades if applicable and the classifications relative to the laboratory normal ranges

For laboratory tests where grades are defined by CTCAE v5.0

- Worst post-baseline CTCAE grade (regardless of the baseline status). Each subject will be counted only once for the worst grade observed post-baseline.
- Shift tables using CTCAE v5.0 grades to compare baseline to the worst on-treatment value

For laboratory tests where grades are not defined by CTCAE v5.0,

- Shift tables using the low/normal/high/ (low and high) classification to compare baseline to the worst on-treatment value.

In addition to the above-mentioned tables and listings, other exploratory analyses, for example, figures plotting time course of raw or change in laboratory tests over time or box plots might be specified in the SAP.

Other safety evaluations

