2.8.5.2 Data analysis

The summaries will include all assessments available for the lab parameter collected no later than 30 days after the last study treatment administration date (see [Section 2.1.1.5](#)).

The following summaries will be produced for hematology and biochemistry laboratory data (by laboratory parameter and treatment):

- Worst post-baseline CTC grade (regardless of the baseline status). Each will be counted only for the worst grade observed post-baseline;
- Shift tables using CTC grades to compare baseline to the worst on-treatment value;
- For laboratory tests where CTC grades are not defined, shift tables using the low/normal/high/(low and high) classification to compare baseline to the worst on-treatment value.

The following listings will be produced for the laboratory data:

- Listing of all CTC grade 3 or 4 laboratory toxicities.

Liver function parameters

Liver function parameters of interest are TBIL, ALT, AST and ALP.

The number (%) of subjects with worst post-baseline values will be summarized:

- ALT or AST > 3×ULN
- ALT or AST > 5×ULN
- ALT or AST > 8×ULN
- ALT or AST > 10×ULN
- ALT or AST > 20×ULN
- TBIL > 2×ULN
- TBIL > 3×ULN
- ALT or AST > 3×ULN & TBIL > 2×ULN
- ALT or AST > 3×ULN & TBIL > 2×ULN & ALP < 2×ULN (potential Hy's law).

Potential Hy's Law events are defined as those subjects with concurrent occurrence of AST or ALT > 3×ULN and TBIL > 2×ULN and ALP < 2×ULN in the same assessment sample during the on-treatment period. Further medical review has to be conducted to assess potential confounding factor such as liver metastases, liver function at baseline, etc.

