AST ↑	U/L	AST	0 - 35 U/L or 0 – 0.58 ukat/L (60 x ukat/L = U/L)	≤ ULN	> ULN – 3.0 x ULN	> 3.0 - 5.0 x ULN	> 5.0 - 20.0 x ULN	> 20.0 x ULN
ALT ↑	U/L	ALT	0 - 35 U/L or 0 – 0.58 ukat/L (60 x ukat/L = U/L)	≤ ULN	> ULN – 3.0 x ULN	> 3.0 - 5.0 x ULN	> 5.0 - 20.0 x ULN	> 20.0 x ULN
Total bilirubin ↑	umol/L	BILI	5.1 – 20.5 umol/L or 0.3 – 1.2 mg/dL (17.1 x mg/dL = umol/L)	≤ ULN	> ULN - 1.5 x ULN	> 1.5 - 3.0 x ULN	> 3.0 - 10.0 x ULN	> 10.0 x ULN
Alk. Phosphatase ↑	U/L	ALP	36 - 92 U/L or 0.5 - 1.5 ukat/L (60 x ukat/L = U/L)	≤ ULN	> ULN - 2.5 x ULN	> 2.5 - 5.0 x ULN	> 5.0 - 20.0 x ULN	> 20.0 x ULN
Creatinine ↑	umol/L	CREAT	61.9 - 115 umol/L or 0.7 – 1.3 mg/dL (88.4 x mg/dL = umol/L)	≤ ULN	> ULN - 1.5 x ULN	> 1.5 - 3.0 x ULN	> 3.0 - 6.0 x ULN	> 6.0 x ULN
Creatinine kinase ↑	U/L	CK	30 – 170 U/L or 0.5 – 2.83 ukat/L (60xukat/L=U/L)	≤ ULN	> ULN - 2.5 x ULN	> 2.5 - 5.0 x ULN	> 5.0 - 10.0 x ULN	> 10.0 x ULN

Final

Lab test (toxicity)	SI unit	Lab test (NCDS)	Normal ranges (Merck manual, July 2015) and conversion factors	CTC Grades ⁽¹⁾				
				0	1	2	3	4
Albumin (Hypoalbuminemia)	g/L	ALB	35 - 55 g/L or 3.5 to 5.5 g/dL	≥ LLN	< LLN - 30 g/L	< 30 - 20 g/L	< 20 g/L	-
Lipase ↑	U/L	LIPASE	<95 U/L or <1.58 ukat/L (60 x ukat/L = U/L)	≤ ULN	> ULN - 1.5 x ULN	> 1.5 - 2.0 x ULN	> 2.0 - 5.0 x ULN	> 5.0 x ULN
Amylase ↑	U/L	AMYLASE	0 - 130 U/L or 0 – 2.17 ukat/L (60 x ukat/L = U/L)	≤ ULN	> ULN - 1.5 x ULN	> 1.5 - 2.0 x ULN	> 2.0 - 5.0 x ULN	> 5.0 x ULN
Calcium (corrected) (Hypercalcemia)	mmol/L	CACALC	2.2 - 2.6 mmol/L or 9 - 10.5 mg/dL (0.2495 x mg/dL = mmol/L)	≤ ULN	> ULN - 11.5 mg/dL > ULN - 2.9 mmol/L	> 11.5 - 12.5 mg/dL > 2.9 - 3.1 mmol/L	> 12.5 - 13.5 mg/dL > 3.1 - 3.4 mmol/L	> 13.5 mg/dL > 3.4 mmol/L
Calcium (corrected) (Hypocalcemia)	mmol/L	CACALC		≥ LLN	< LLN - 8.0 mg/dL < LLN - 2.0 mmol/L	< 8.0 - 7.0 mg/dL < 2.0 - 1.75 mmol/L	< 7.0 - 6.0 mg/dL < 1.75 - 1.5 mmol/L	< 6.0 mg/dL < 1.5 mmol/L
Magnesium ⁽²⁾ (Hypermagnesemia)	mmol/L	MG	0.62 – 0.99 mmol/L or 1.5 – 2.4 mg/dL (0.4114 x mg/dL = mmol/L)	≤ ULN	> ULN - 3.0 mg/dL > ULN - 1.23 mmol/L	-	> 3.0 – 8.0 mg/dL > 1.23 – 3.3 mmol/L	> 8.0 mg/dL > 3.3 mmol/L
Magnesium ⁽²⁾ (Hypomagnesemia)	mmol/L	MG		≥ LLN	< LLN - 1.2 mg/dL < LLN - 0.5 mmol/L	< 1.2 - 0.9 mg/dL < 0.5 - 0.4 mmol/L	< 0.9 - 0.7 mg/dL < 0.4 - 0.3 mmol/L	< 0.7 mg/dL < 0.3 mmol/L
Glucose (Hypoglycemia)	mmol/L	GLUCSN/ GLUCSF		≥ LLN	< LLN - 55 mg/dL < LLN - 3.0 mmol/L	< 55 - 40 mg/dL < 3.0 - 2.2 mmol/L	< 40 - 30 mg/dL < 2.2 - 1.7 mmol/L	< 30 mg/dL < 1.7 mmol/L

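### As written, the SAP gives high glucose no by-arm summary and no laboratory listing, because Table 5-3 grades glucose only for hypoglycemia

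*SAP*

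**What the plan says.** **Grading (SAP 2.8.5.1 and 5.3.1).** Laboratory grades are assigned by program from observed values, without clinical assessment. Both sections carry the rule "A severity grade of 0 will be assigned for all non-missing lab values not graded as 1 or higher". For tests that CTCAE v5.0 does not grade, "results will be graded by the low/normal/high classifications based on laboratory normal ranges". For tests graded both low and high, "summaries will be done separately and labeled by direction".

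**Table 5-3.** Glucose has one row, hypoglycemia. Its grade 0 runs from the lower limit of normal upward, and grades 1 to 4 run downward. Corrected calcium, magnesium, potassium and sodium each have a row for both directions.

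**Outputs (SAP 2.8.5.2).** Graded tests get a worst post-baseline grade table and a grade shift table. The alternative is limited: "For laboratory tests where CTC grades are not defined, shift tables using the low/normal/high/(low and high) classification". One laboratory listing is named: "Listing of all CTC grade 3 or 4 laboratory toxicities".

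**Protocol 12.5.2.** All laboratory data are to be listed by arm, subject and time, marked against the normal range. Summary statistics by treatment and visit are also planned. A general sentence says "Shift tables using the low/normal/high/ (low and high) classification will be used to compare baseline to the worst on-treatment value", but later bullets in the same section limit that table to tests without CTCAE grades.

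**SAP section 4.** No departure from the protocol's analyses is declared.

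**The concern.** The fallback to low/normal/high works test by test, while Table 5-3 grades direction by direction. A test with one graded direction falls between the two: it counts as graded, so it loses the fallback, yet its other direction has no grade. For glucose the lost direction is the high one.

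The protocol itself treats high glucose as relevant. "Fasting plasma glucose" is capped at 160 mg/dL (8.9 mmol/L) for entry (section 5.1), and controlled type I diabetes on stable insulin is permitted (section 5.2). Glucose is in the chemistry panel (Table 8-6), scheduled at screening, each cycle and end of treatment until amendment 03 (Table 8-2). While capmatinib was being given, the toxicity guidance included prednisone at 1-2 mg/kg for cardiac events (Table 6-6) and pneumonitis (Table 6-7), and systemic steroids can raise glucose.

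Enrollment was halted because the combination was poorly tolerated, so the safety comparison is a main product of the study. The laboratory tables named in the SAP would give the reader no view of high glucose in either arm.

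**Working it through.** No sample size, power or event count is involved. The check traces a glucose value through the SAP's rules, then sets the SAP's outputs beside the protocol's.

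**Step 1: grade under Table 5-3.** Cut-offs in mmol/L, with v the glucose value:

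- grade 4 if v < 1.7
- grade 3 if 1.7 ≤ v < 2.2
- grade 2 if 2.2 ≤ v < 3.0
- grade 1 if 3.0 ≤ v < LLN
- grade 0 otherwise

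No glucose normal range is legible in the table, so LLN is assumed to lie between 3.3 and 4.1 (tried at 3.3, 3.9 and 4.1). All three give the same result:

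| Glucose (mmol/L) | Grade |
|---|---|
| 1.5 | 4 |
| 2.0 | 3 |
| 2.5 | 2 |
| 3.2 | 1 |
| 5.0 | 0 |
| 8.9 | 0 |
| 13.9 | 0 |
| 27.8 | 0 |
| 40.0 | 0 |

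A normal value and a very high one are indistinguishable.

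**Step 2: follow a high value through SAP 2.8.5.2.**

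- Worst-grade table: grade 0, in the hypoglycemia row.
- Grade shift table: a subject whose baseline is not low shows grade 0 to grade 0.
- Low/normal/high shift table: not produced, since glucose has a CTC grade.
- Grade 3 or 4 listing: not reached.

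**Step 3: apply low/normal/high instead.** With an upper limit assumed between 5.6 and 7.8 mmol/L (tried at 5.6, 6.1 and 7.8), 5.0 is normal and 8.9, 13.9 and 27.8 are high in every case. The classification the SAP already uses for ungraded tests would show what the grade tables do not.

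**Step 4: SAP beside protocol.**

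| Output | Protocol 12.5.2 | SAP 2.8.5.2 |
|---|---|---|
| Listing | All laboratory data, marked against normal range | Grades 3 and 4 only |
| Statistics by visit | Planned | Not named; only the general statement on descriptive statistics in SAP 2.1 |
| Low/normal/high shift | General sentence, then limited to ungraded tests | Ungraded tests only |

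The listing is a clear narrowing. For the shift table the protocol can be read either way, so a broken commitment cannot be shown there.

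**Step 5: which data.** From amendment 03, laboratory results are no longer captured on the eCRF (protocol 8.4). The affected results are those recorded before then, in the Safety set. With 76 subjects randomized (51 and 25), that is the most who could contribute.

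**The case against.** The strongest reply is that high glucose will be visible elsewhere. The protocol's full listing would show it, and its summary statistics by visit include the maximum, which an extreme value would move. Because the SAP declares no change, both outputs could be said to stand. Clinically significant laboratory findings must also be recorded as adverse events (protocol 8.4 and 8.4.1), and SAP 2.8.1 lists all adverse events and summarizes the on-treatment ones by arm.

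Much of this stands. A reader might infer that hyperglycemia would be listed nowhere, or that no planned output could reveal it. The documents do not support that; what is supported is its absence from the laboratory grade tables and laboratory listing that the SAP specifies. The SAP sets the methods for the CSR, and it names a narrower listing. Declaring no change does not settle which listing is produced, and the output shells that might settle it are not available. Adverse-event recording depends on investigator judgment, whereas laboratory grading is meant to work from observed values alone. A full listing is also not a comparison by arm.

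A reader might also infer that the SAP labels high glucose as non-toxic. It does not: grade 0 is correct for a hypoglycemia row. The defect is the missing high side.

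Two further replies carry less weight. SAP 5.3.1 allows the latest version of the grading document to be used at analysis, but nothing says that version adds a high-glucose row. The fallback might be read as covering an ungraded direction, but its wording refers to tests, so the text would at best be ambiguous. Whether CTCAE v5.0 gives numeric grades for high glucose cannot be settled from these documents, and the point does not need it.

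**Conclusion.** The point holds as a gap in safety reporting. Applied as written, the SAP reduces every high glucose result to grade 0 for hypoglycemia, with no high-side summary by arm and no entry in its laboratory listing. The listing also departs from protocol 12.5.2 without being declared.

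The size is known only as a rule. All high glucose results on the eCRF before amendment 03 took effect are affected, but the documents do not say how many there are. Nor do they show that the arms differ in glucose or in steroid use, so a hidden imbalance should not be inferred. The primary endpoint and other efficacy analyses are unaffected.

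The conclusion assumes that Table 5-3 is used as printed and that the fallback applies per test. It does not depend on the assumed normal limits, since every value tried at 8.9 mmol/L or above gave the same answer throughout.

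**What to change.** - In SAP 2.8.5.1, 2.8.5.2 and 5.3.1, state that the grade-0 rule applies only to the direction that Table 5-3 grades.
- Add a low/normal/high shift table for glucose, baseline to worst on-treatment value, by arm. Show fasting and non-fasting results separately where the data allow. The two glucose codes in Table 5-3 (GLUCSN and GLUCSF) suggest this is feasible, though the SAP does not define them.
- Restore the protocol's listing of all laboratory data marked against normal ranges, or declare the narrower listing as a change in SAP section 4.

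A count of post-baseline values above 8.9 mmol/L is optional. That figure is a fasting limit for entry, and post-baseline samples may be non-fasting.

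The cost is a few sentences, one table and one listing, all from data already collected. SAP section 1 provides the route: an amendment before database lock, an addendum after it. Other tests graded in one direction, such as platelets or AST, would share the clarified grade-0 wording but need no new table for this purpose. The small downside is that non-fasting samples will add mild highs in both arms.
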